TESTING: TElehealth based Synchronous navigation To Improve molecularly-informed care for patients with IuNG cancer

Principal Investigator:	[name], MPH Associate Professor of Medicine [contact] [contact]
Funding Agency:	National Institutes of Health
NIH Grant Number:	P50CA271338
IRB Protocol Number:	852857
UPCC Protocol Number:	22522
ClinicalTrials.gov Identifier:	NCT05790460
Version Date:	August 18, 2023 (Version 2)

Protocol Summary

Title	TESTING: Telehealth based Synchronous navigation To Improve molecularly-informed care for patients with lung cancer
Short Title	TESTING
Principal Investigator	[name], MPH
Co-Investigators	[name], MTR [name], MS [name] [name], MBA [name], MSW, MPH [name], MPH [name] [name], MPH, MBA, MBBS [name] [name], OCN [name] [name] [name] [name], PhD
Design	Randomized, two-arm clinical trial
Objectives	
 1. In a randomized pilot trial of patients with suspected locally advanced/metastatic NSCLC, test the effectiveness of enhanced synchronous telehealth nurse navigation, compared to usual care nurse navigation, to increase timely molecularly-informed treatment recommendations through early integration of concurrent molecular testing. 2. Evaluate contextual mechanisms contributing to the effectiveness of synchronous telehealth nurse navigation.
Trial Duration	30 months
Study Sites	University of Pennsylvania Health System (UPHS) sites: Hospital of the University of Pennsylvania Pavilion (HUP) – East Hospital of the University of Pennsylvania (HUP) Pennsylvania Hospital (PAH) Penn Presbyterian Medical Center (PPMC)
Sample Size	Objective 1: 138 patients Objective 2: 20-30 patients and 10-15 clinicians/clinical leaders
Patient Eligibility	Patients will be eligible for the randomized clinical trial if they: 
 are aged 18 years or older

	
 b) based on cross-sectional imaging, are suspected to have locally advanced/metastatic NSCLC (as determined by the evaluating clinician) c) are scheduled for an appointment in the lung cancer evaluation clinic.
Clinician Eligibility	Clinical leaders and clinicians (including physicians, advanced practice providers, and other clinicians) who treat lung cancer at Penn Medicine.
Interventions	Eligible patients will be individually randomized to one of two arms: 
 1. Usual care – standard nurse navigation. 2. Enhanced nurse navigation – synchronous telehealth nurse navigation visit prior to biopsy.
Outcomes	
Objective 1: Receipt of a molecularly-informed treatment recommendation for patients with metastatic NSq NSCLC at the time of the patient's initial oncology visit.
 
Secondary Outcomes:
 
 1. Rate of telehealth visit completion 2. Rate of completion of comprehensive molecular testing (tissue and/or plasma testing) prior to initiation of first line therapy 3. Identification of one or more targetable mutations 4. Timeliness of molecularly-informed treatment recommendation 5. Overall survival 6. Intervention costs 7. Proportion of patients with diagnosis other than metastatic nonsquamous NSCLC (Telehealth arm only) 8. Time to treatment initiation 
Objective 2: Individual and contextual factors (e.g., treatment knowledge, medical mistrust, clinical beliefs, organizational climate, patient-centered communication, financial toxicity, and knowledge of genetic testing) shaping trial effectiveness and patient experience.

Primary Analysis	
Objective 1: Intention-to-treat (ITT) analyses for effectiveness using logistic regression.
 
Objective 2: Mixed methods evaluation of descriptive survey data and thematically coded interview data.

Study Oversight	[name] (PI) will be responsible for monitoring the trial and ensuring subject safety, as well as the integrity of the interventions and the data collected. Trial oversight will be conducted by the University of Pennsylvania Institutional Review Board.

Contents

Principal Investigator:	1
Funding Agency:	1
Protocol Summary	2
1. BACKGROUND AND RATIONALE	5
2. OBJECTIVES	6
2.1 Primary Objectives	6
2.2 Primary Outcomes	6
2.3 Secondary Outcomes	6
3. STUDY POPULATION	6
3.1 Target Population	6
3.2 Inclusion Criteria	6
4. STUDY DESIGN	7
4.1 Preliminary Studies	7
4.2 Overview	7
4.3 Study Duration and Timeline	10
4.4 Study Setting	10
5. STUDY PROCEDURES	11
5.1 Recruitment and Retention	11
5.2 Informed Consent	11
5.3 Compensation	12
5.4 Measures and Endpoints	13
5.5 Sources of Materials	14
6. STATISTICAL DESIGN AND POWER	14
6.1 Sample Size	14
6.2 Analysis Plan	14
6.2.1 Objective 1 Primary Analyses	14
6.2.2 Objective 1 Secondary Analyses	15
6.2.3 Objective 1 Exploratory Analyses	15
6.2.4 Objective 2 Analyses	15

1. BACKGROUND AND RATIONALE

The present pilot project is an initiative being conducted by the University of Pennsylvania Telehealth Research Center of Excellence (TRACE). TRACE strives to advance care delivery research through design and testing of innovative telehealth strategies to improve effectiveness and equity across the cancer care continuum.

Precision cancer medicine holds great promise for improving lung cancer outcomes and survival, but its promise will only be realized if patients have broad access to a singular and essential precision component: molecular testing.¹ For non-small cell lung cancer (NSCLC), the past decade has been marked by a steady increase in the number of therapeutically actionable molecular targets used to guide management.^{2,3} These therapeutically actionable mutations are present in approximately 30-40% of patients with non-squamous (NSq) NSCLC. At present, over a dozen orally administered targeted therapy regimens for metastatic NSq NSCLC require molecular testing for specific targetable genomic alterations.⁴ National guidelines currently recommend that comprehensive molecular testing be performed for all newly diagnosed metastatic NSq NSCLC patients as standard of care.^{4,5} Despite the importance of molecular testing in patients with metastatic NSq NSCLC, considerable barriers to timely completion of comprehensive molecular testing prior to initiation of systemic therapy exist, with concerning evidence of disparities by race. In a real-world analysis of 14,768 patients, next-generation sequencing (NGS) was performed among 50.1% of white patients and only 39.8% of Black patients ($p < 0.0001$), even though prevalence of mutations does not vary by race.⁶

Testing of tumor tissue has traditionally been the preferred source of molecular testing, but tumor tissue may be insufficient or unavailable for testing due to factors including location of disease or quality of biopsy.^{7,8} Even when feasible, the “turn-around-time” for tumor tissue testing frequently requires 3-4 weeks.⁷ These barriers hinder the extent to which patients and clinicians can make guideline-concordant treatment decisions at the time of the initial in-person medical oncology visit, delaying initiation of cancer therapy and diminishing both patient and clinician satisfaction and quality of care. For metastatic NSq NSCLC, treatment initiation without molecular testing or treatment delays of any duration can be consequential, degrading the effectiveness of life-extending therapy, and can weigh heavily on patients and clinicians.^{9,10} Our team, and others, have shown that the addition of concurrent plasma-based molecular testing may help address the crucial molecular under-testing gap by offering an approach that is fast and convenient, especially for patients where tissue is unavailable or inaccessible. Plasma-based molecular testing is a complementary mechanism to obtain molecular results upon initial diagnosis, is included in national guidelines, and could be particularly meaningful to address the inequities faced by patients from communities that experience health disparities.^{11,12}

The overarching goal of this pilot trial is to design and test a nurse navigation intervention delivered via telehealth for patients with suspected locally advanced/metastatic NSCLC to improve timely molecularly-informed treatment recommendations through early integration of concurrent molecular testing (i.e., tumor tissue and plasma-based molecular testing or plasma only when tumor tissue is insufficient/unavailable). Our central hypothesis is that providing telehealth nurse navigation to support completion of concurrent molecular testing will result in higher rates of comprehensive testing, improved timeliness of molecularly-informed treatment recommendations (primary endpoint), earlier initiation of molecularly-informed treatment, more meaningful patient-clinician communication, and higher levels of overall satisfaction among patients and clinicians. Drawing from systematic evidence on the role of navigation for coordination of cancer care and informed by insights from communication science and behavioral economics, the specific telehealth strategy to be tested is synchronous telehealth nurse navigation in combination with default ordering of plasma-based testing. This trial will allow us to assess multilevel determinants shaping the effectiveness and equity of telehealth strategies for cancer treatment initiation.

2. OBJECTIVES

2.1 Primary Objectives

Objective 1: In a randomized pilot trial of patients with suspected locally advanced/metastatic NSCLC, test the effectiveness of enhanced synchronous telehealth nurse navigation, compared to usual care nurse navigation, to increase timely molecularly-informed treatment recommendations through early integration of concurrent molecular testing.

Objective 2: Evaluate contextual mechanisms contributing to the effectiveness of synchronous telehealth nurse navigation.

2.2 Primary Outcomes

Objective 1: Receipt of a molecularly-informed treatment recommendation for patients with metastatic NSq NSCLC at the time of the patient's initial oncology visit.

Objective 2: Individual and contextual factors (e.g., treatment knowledge, medical mistrust, clinical beliefs, organizational climate, patient-centered communication, financial toxicity, and knowledge of genetic testing) shaping trial effectiveness and patient experience.

2.3 Secondary Outcomes

Objective 1: Secondary outcomes include:

- 1) Rate of telehealth visit completion
- 2) Rate of completion of comprehensive molecular testing (tissue and/or plasma testing) prior to initiation of first line therapy
- 3) Identification of one or more targetable mutations
- 4) Timeliness of molecularly-informed treatment recommendation
- 5) Overall survival
- 6) Intervention costs
- 7) Proportion of patients with diagnosis other than metastatic NSq NSCLC (telehealth arm only)
- 8) Time to treatment initiation

3. STUDY POPULATION

3.1 Target Population

Objective 1: The target population is 138 patients with suspected locally advanced/metastatic NSCLC.

Objective 2: The target population is 20-30 patients who participate in the pilot trial and 10-15 clinicians or clinical leaders.

3.2 Inclusion Criteria

Objective 1:

Patients will be eligible for the randomized clinical trial if they:

- a) are aged 18 years or older
- b) based on cross-sectional imaging, are suspected to have locally advanced/metastatic NSCLC (as determined by the evaluating clinician)
- c) are scheduled for an appointment in the lung cancer evaluation clinic.

Objective 2:

Patients will be eligible if they were selected for participation in the pilot trial. Clinicians will be eligible if their area of expertise relates to the protocol topic (e.g., oncologists, nurses, clinical leads).

3.3 Exclusion Criteria

Patients will be ineligible for the pilot randomized clinical trial if they:

- a) are not suspected to have locally advanced/metastatic NSCLC
- b) have a concurrent active malignancy.

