Patients in the intervention arm will be scheduled for an enhanced synchronous telehealth visit with a trained lung cancer nurse navigator prior to tissue biopsy. The enhanced synchronous telehealth visit will ideally occur between the initial clinical appointment and diagnostic biopsy (typically a period between two and seven days). In addition to the activities conducted as part of usual care, the nurse navigator will: 1) provide more detailed and individualized education on lung cancer and the rationale for comprehensive molecular testing, including plasma-based tests; and 2) if the patient agrees to testing, pend a default order for plasma-based molecular testing (if not already ordered) for the clinician to sign and arrange for phlebotomy to be performed during the periprocedural window associated with the patient's tissue biopsy.

Objective 2: Using rigorous approaches proven successful in our prior work,^{15,16} we will recruit 20-30 patient participants of the primary trial and 10-15 clinicians and clinical leaders to complete semi-structured interviews following the active trial period.

Patients: We will oversample for Black patients to understand effectiveness by race/ethnicity and stratify by trial outcome and study arm to understand factors contributing to both success and failure (e.g., primary endpoint) in either group (5-10 patient in each stratum). Trial participants will be invited in randomly selected batches each month (to enhance capture over time) until we reach our target sample of approximately 20-30 patients. Patients will be invited to participate in interviews via email and/or letter within 6 weeks of their in-person oncology visit.

Clinicians: Recruitment for clinicians will be similar to the procedure for patients, except we will wait until the completion of the full trial to conduct interviews to avoid potential contamination. Clinicians will be purposively sampled by clinical role (e.g., oncologists, nurses, clinical leads) to enhance variation and invited via email. Recruitment will continue until we reach our target sample of 10-15 clinicians.

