5.4 Measures and Endpoints

Objective 1: The specific outcomes align with 5 key endpoints (access, quality, outcomes, equity, and efficiency). The primary endpoint is receipt of a molecularly-informed treatment recommendation at the time of the patient's initial in-person oncology visit, measured up to 12 weeks from randomization. This outcome encompasses successful completion of comprehensive molecular testing and the ability of the patient and oncology care team to have all necessary information to collaboratively arrive at the optimal treatment approach. We anticipate that approximately 10% of patients randomized to usual care will be able to receive a molecularly-informed treatment recommendation at initial visit – these include patients in whom tissue was successfully tested and identified a targetable mutation prior to referral. We anticipate this will be substantially improved with enhanced nurse navigation (See Section 6.1 Sample Size). The primary endpoint will be assessed by review of clinician documentation (e.g., progress notes) within the electronic medical record (EMR) on the day of the initial visit.

Secondary outcomes include:

- 1) Operational endpoints:
 - a. Rate of completion of telehealth visit defined as successful completion of a nurse navigator telehealth visit prior to biopsy, measured up to 3 weeks from randomization.
 - b. Rate of completion of comprehensive molecular testing (tissue and/or plasma testing) prior to initiation of first line therapy, measured up to 12 weeks from randomization.
- 2) Clinical endpoints:
 - a. Time from randomization to molecularly-informed treatment recommendation, measured up to 12 weeks from randomization.
 - b. Proportion of participants with one or more targetable mutations, measured up to 12 weeks from randomization.
 - c. Overall survival, measured as 1-year overall survival from time of randomization to death from any cause.
 - d. The proportion of enrolled patients with a diagnosis other than metastatic NSq NSCLC (telehealth arm only), measured at 12 weeks from randomization.
 - e. Time from randomization to treatment initiation, measured up to 12 weeks from randomization.
- 3) Cost outcomes:
 - a. Intervention costs (measured using a pragmatic method to capture and analyze all system-level resources, such as personnel time and patient outreach costs) that are needed to deploy telehealth strategies in routine care.¹⁹

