6. STATISTICAL DESIGN AND POWER

6.1 Sample Size

Objective 1: Sample size is based on estimates of receiving a molecularly-informed treatment recommendation at the initial oncology visit. Based on our prior studies, we anticipate this will occur in 10% of patients in the usual care arm. This pilot study is designed to detect an absolute increase of 20% in our primary outcome for patients in the intervention arm. With a sample size of 124 participants and a two-sided alpha, we will have >80% power to detect an increase of this magnitude. Given the potential for drop-out of patients following randomization, we have increased the estimate by 10%, leading to a final sample size of 138 participants (69 in each arm). Although a difference <20% in our primary outcome rate may be clinically meaningful, this sample size is an optimal balance to allow an assessment of our primary and secondary outcomes and assess for mechanisms of action. Study outcomes will be used to preliminarily assess effectiveness across all outcome domains to inform the design of future studies, including a pragmatic trial, if warranted.

Objective 2: Proposed sample size is based on the estimated number of interviews needed to reach data saturation within each group and by intervention outcome to support mixed methods evaluation; however, interviews will continue until saturation is achieved.^{16,21}

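### Eligibility does not require the diagnostic biopsy to be still ahead at randomisation, although the intervention visit and its completion outcome are defined as before biopsy

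*Combined protocol and SAP*

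**What the plan says.** **Eligibility.** Section 3.2 asks for age 18 or over, suspicion of locally advanced or metastatic NSCLC on cross-sectional imaging, and that patients "are scheduled for an appointment in the lung cancer evaluation clinic". Section 3.3 excludes patients without that suspicion and those who "have a concurrent active malignancy". Neither list refers to a completed biopsy or to molecular results.

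**Intervention.** Section 4.2 describes an "enhanced synchronous telehealth visit with a trained lung cancer nurse navigator prior to tissue biopsy", with the plasma draw placed in the window around that biopsy. Section 5.4, secondary outcome 1a, counts a telehealth visit as completed only if it took place before biopsy.

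**Timing.** Section 4.2 allows randomisation before or shortly after the clinic appointment and puts the usual interval from appointment to biopsy at two to seven days. Section 5.1 screens clinic schedules weekly and confirms eligibility from the medical record.

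**Analysis and size.** Section 6.2.1 makes the primary analysis an unadjusted intention-to-treat logistic regression. Section 6.1 says of the primary outcome that "we anticipate this will occur in 10% of patients in the usual care arm", targets a 20-point increase, and enlarges the sample only for 10% drop-out.

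**The concern.** The intervention is tied to a moment in the diagnostic pathway, but the entry criteria are not. With weekly screening, randomisation permitted after the appointment, and biopsy possibly two days after it, someone can be randomised after biopsy even on the standard pathway. Someone who arrives with an outside biopsy or molecular report is not excluded by any explicit criterion either.

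Two things are at stake:

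- **Feasibility.** A patient biopsied before randomisation is a non-completer for outcome 1a whatever the navigator does. The completion rate then mixes failure to deliver the visit with patients for whom it was never possible. That matters in a pilot meant to inform a later trial.
- **Effectiveness.** A patient whose molecular testing is complete at randomisation has a primary outcome that allocation can hardly change. Such patients add near-identical outcomes to both arms and take up places among the 138.

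**Working it through.** **Inputs.** From section 6.1: 10% in usual care, a 20-point increase (so 30%), 124 evaluable patients (62 per arm), 10% drop-out, 138 in total (69 per arm). The test is two-sided, but the alpha level is not stated; 0.05 is assumed. The share f of randomised patients whom the intervention cannot help is not given; 5%, 10% and 20% are assumed for illustration.

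**Step 1: reproduce the plan.** With pooled variance and no continuity correction, where p̄ is the mean of p1 and p2,

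n per arm = [1.960·√(2p̄(1−p̄)) + 0.842·√(p1(1−p1) + p2(1−p2))]² / (p2−p1)²

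For 0.10 v 0.30, p̄ = 0.20: [1.960·√0.32 + 0.842·√0.30]² / 0.04 = (1.109 + 0.461)² / 0.04 = 61.6, so 62 per arm and 124 in total. Drop-out: 124/0.9 = 137.8, so 138. Both figures match the plan.

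Power at 62 per arm = Φ{[0.20·√62 − 1.109] / √0.30} = Φ{(1.575 − 1.109)/0.548} = Φ(0.851) = 80.3%. This agrees with the claim that "we will have >80% power to detect an increase of this magnitude", with little to spare.

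**Step 2: dilution if the 20 points applies only to reachable patients.** Suppose the unreachable share f has 10% success in both arms. Then p2 = 0.10 + 0.20·(1−f), and the intention-to-treat difference is 20·(1−f) points.

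| f | Patients of 138 | Difference (points) | Power, 62 per arm | Power, 69 per arm | Total N for 80% power: evaluable / with drop-out |
|---|---|---|---|---|---|
| 0 | 0 | 20 | 80.3% | 84.3% | 124 / 138 |
| 5% | about 7 | 19 | 76.8% | 81.1% | 136 / 152 |
| 10% | about 14 | 18 | 72.9% | 77.5% | 148 / 165 |
| 20% | about 28 | 16 | 64.3% | 69.0% | 180 / 200 |

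The 69-per-arm column applies if nobody drops out. As a check at f = 10%: p̄ = 0.19, and Φ{[0.18·√62 − 1.960·√0.3078] / √0.2916} = Φ{(1.417 − 1.087)/0.540} = Φ(0.611) = 72.9%.

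The 10% success rate for unreachable patients is itself an assumption. At 50% in both arms, power at 62 per arm is 73.6%, 66.7% and 52.9% for the same values of f.

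**Step 3: if 20 points is the whole-arm effect.** The comparison stays 10% v 30% and power stays 80.3%. Reachable patients must then gain 20/(1−f) points: 21.1, 22.2 and 25.0 at f = 5%, 10% and 20%.

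**Step 4: ceiling on visit completion.** If a share b of the telehealth arm is already biopsied at randomisation, completion cannot exceed 1−b: 95%, 90% and 80% for b = 5%, 10% and 20%. The shares b and f need not be equal. A biopsied patient without molecular results counts fully in b but not necessarily in f.

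**The case against.** **Most patients described are pre-biopsy.** Eligibility rests on suspicion from imaging, section 4.2 puts the clinic appointment before biopsy, and section 5.1 schedules the visit between the two. This stands as a reason to expect f to be small. It does not close the gap: suspicion is defined by imaging rather than by the absence of tissue, and randomisation may follow the appointment.

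**A reader might infer that the plan knowingly enrols already-tested patients.** Section 5.4 says of the expected usual-care successes that "these include patients in whom tissue was successfully tested and identified a targetable mutation prior to referral", and section 4.2 has the navigator pend a plasma order only where none exists. Neither supports that inference. The referral may be the one to medical oncology, which can come after randomisation. The second remark describes the position at the navigator visit, which also follows randomisation, and an order is not a result.

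**A reader might also infer that the intervention can do nothing for anyone already biopsied.** That is too strong. Section 1 says tissue results frequently take 3-4 weeks, and section 4.2 asks that usual-care patients have no plasma testing before the first oncology visit. A biopsied patient without results could therefore still gain from an earlier draw. Dilution is firm only for completed testing; for other biopsied patients the firm point is that outcome 1a cannot be met.

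**The 20 points may already be net of these patients.** Section 6.1 states the increase for the intervention arm, which can be read as the whole randomised arm. On that reading no power is lost. The documents do not settle it.

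**As-treated analyses are planned (section 6.2.2).** They partly address non-receipt, but they do not identify the corresponding usual-care patients, so they do not replace a criterion or a baseline record that applies to both arms.

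**Conclusion.** The gap holds: as written, sections 3.2 and 3.3 can admit patients for whom the visit, as sections 4.2 and 5.4 define it, is no longer possible. The direction is clear. Completion is lowered for a reason unrelated to feasibility, and patients with completed testing pull the intention-to-treat difference toward zero.

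The size is not established. A fall in power from 80.3% to 76.8%, 72.9% or 64.3% requires f of 5%, 10% or 20%, a 20-point gain confined to reachable patients, 10% success in both arms among the rest, and alpha 0.05. If the 20 points already describes the whole arm, power is unchanged. It would therefore be wrong to conclude that the trial is underpowered on this account. This is a cheap improvement, not a defect that undermines the design.

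**What to change.** Add to section 3.3: *have already undergone the diagnostic biopsy for the current suspected cancer, or have tissue or plasma molecular results available, before randomization.* Confirm it at the record review in section 5.1. Do not exclude for a test merely ordered, because section 4.2 provides for that situation. A patient biopsied after randomisation but before the visit stays in the trial and counts as a genuine non-completion.

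State in section 6.1 that the 10% rate and the 20-point increase refer to this population. If the 10% includes patients with results before randomisation, the study team must restate it from its own data; the documents give no figure from which to derive it.

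For patients already enrolled, record biopsy and testing status at the date of randomisation in both arms and report f. Because that status precedes allocation, results can also be shown for patients still awaiting biopsy without breaking the randomised comparison.

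Cost: a one-line amendment and one extra item in a review that already takes place. Accrual would be slightly slower, and results would apply only to patients awaiting biopsy, which is the group the visit is designed for.
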